#### 1. BACKGROUND AND RATIONALE

**Elderly, an at-risk group:** Life expectancy among the elderly is rising globally, including Singapore. A longer life places the elderly at risk of chronic diseases, which often entail long term drug therapy. The elderly, thus, with their co-morbidities, have a higher risk of polypharmacy, which in turn is associated with a greater likelihood of medication non-adherence. Further, given their exposure to polypharmacy, the elderly often have to navigate through multiple PMLs on a daily basis.

[figure not shown]
Prescription Medication labels (PMLs): PMLs, affixed on packets/bottles of prescription medications, are the **patients' main source of medication-related instructions in Singapore**. Many patients in Singapore receive no information from healthcare providers except the instructions on PMLs, further highlighting their relevance. Correct understanding of PMLs is key to medication safety and adherence, esp. for the elderly. Difficulty in finding and comprehending information on PMLs can adversely affect patient safety and adherence to instructions. Although local data on medication errors attributed to PML misunderstanding are lacking, a study elsewhere reported that majority of outpatient medication errors are due to patients' inability to take their own medications as intended. And, poor medication safety and adherence result in poor clinical outcomes and unnecessary healthcare costs. Thus, ensuring that patients, esp. the elderly, correctly understand their PMLs is vital.

A key barrier faced by elderly Singaporeans in reading and understanding their PMLs is the language commonly used on them, English. A study of a national sample of elderly Singaporeans found that despite 69% being unable to read English, their PMLs were mostly only in English (81%). This discrepancy places the elderly at risk of medication errors, non-adherence, and side effects. At the same time, many elderly Singaporeans who cannot read English can read another official language (Mandarin Chinese/Malay/Tamil). This highlights a **direct and** innovative approach to make existing PMLs patient-centric, i.e., add another preferred language – bilingual PMLs. A study led by the project mentor showed that bilingual PMLs lead to a substantial increase in understanding of PML content among the elderly, supporting its real-world utility. And, patient feedback collated by the project Co-Is (SGH pharmacists) strongly suggests the need for bilingual PMLs. However, adoption of bilingual PMLs in Singapore has been slow. One reason is the lack of evidence for their positive impact on important medication-related outcomes, i.e., medication management self-efficacy and medication adherence. The proposed study will provide rich preliminary data that will enable the conduct of a larger RCT on the impact of bilingual PMLs on these very medication-related outcomes.

Conceptual Framework: Our framework focuses on the relationship between attainment of knowledge (medication knowledge via PMLs), medication management self-efficacy and engagement in self-care behaviours (i.e. medication taking behaviour) as a process that ultimately affects our key outcome, medication adherence. (Figure 1)

Attainment of knowledge: Cognitive processes (i.e., perception, memory, problem solving, etc.) generally subsume the concept of understanding. In investigating PML understandability, understanding has been defined as the capacity to describe – using one's own words (i.e., more than simply reading) – how a medication should be taken. In context of our study, bilingual PMLs will facilitate understanding among

the elderly, resulting in attainment of medication knowledge. Research shows that lack of knowledge is likely to affect individual's self-

efficacy to adhere to complex regimens. Further, it has been suggested that interventions aimed at improving medication adherence should design interventions targeted at increasing knowledge and self-efficacy.

*Medication management self-efficacy:* Self-efficacy, drawing on the social-cognitive theory, is defined as "the individual's belief in their capabilities to implement a specific/a set of behaviour(s)". More specifically, in context of medication management, self-efficacy refers to a belief in the patient's capacity to follow a prescribed medical regimen when faced with challenging situations. Several studies have found a positive link between medication management self-efficacy and medication adherence. Self-efficacy directly affects health behaviours. Patients with higher self-efficacy are more likely to have better adherence to self-care tasks, such as medication taking.

*Medication adherence:* Adherence to medications is critical to ensuring optimal health outcomes, yet around 50% of patients do not do so. In the United States, up to two-thirds of all medication-related hospitalizations result from poor medication adherence. Singaporean data also portrays low medication adherence rates. Medication adherence is influenced by patient, physician, medication and health-system factors. Our study, by initiating evidence gathering for the impact of bilingual PMLs on medication adherence, concurrently addresses two such factors, a patient factor, i.e., language reading ability, and a health-system factor, particularly important in Singapore, i.e., PMLs.

**Overall, we conceptualise that** by facilitating attainment of medication knowledge (better understanding via bilingual PMLs), patients will advance their medication management self-efficacy, leading to engagement in medication taking behaviour, ultimately resulting in medication adherence.

Need for rigorous PML intervention studies: A recent review on the impact of improved PMLs concluded that intervention studies that test PML improvements in a rigorous manner are lacking. It also recommended that future studies should extend research to outcomes more proximal to medication taking – medication adherence and medication management self-efficacy. In Singapore, the only published PML intervention did show bilingual PMLs (vs English PMLs) to increase PML understanding. However, it, again, did not assess medication adherence and medication management self-efficacy. Thus, rigorous intervention studies that assess the impact of improved PMLs on a range of medication-related outcomes are needed.

Our proposal is the *first step* towards a well-informed, rigorous intervention study or RCT that will provide concrete evidence on the impact of the provision of bilingual PMLs on key medication-related outcomes – medication adherence, medication management self-efficacy, and PML understanding. The experience gained, and data collected, through the conduct of the 2 pilot trials, funded through the current proposal, will allow us to choose the optimal trial design, and refine protocols for recruitment, engagement and retention of study participants for the larger RCT as well as determine variability in outcomes so that the larger RCT is appropriately powered to detect meaningful differences in the outcomes – an immediate output of our proposed project will be a grant proposal to a national level grant mechanism for the conduct of the larger RCT. Eventually, the 2 pilot trials, and the subsequent larger RCT, will contribute to implementing patient-centered PMLs.

#### 2. HYPOTHESIS AND OBJECTIVES

Since the proposed study will collect preliminary data for informing the larger RCT, it does not aim to detect a significant difference in the trial outcomes in either pilot trial. Rather, its specific aims are:

AIM 1. To assess the feasibility of administering the intervention in the 2 "pilot" RCT versions. The proposed formative study will inform which of the 2 pilot trials will be scaled up and tested in the larger RCT. It will also result in finalization of the intervention and measurement material. AIM 2. To refine protocols for study participant recruitment, engagement and retention. AIM 3. To gain experience with and refine measurement of the medication-related outcomes.

A key outcome, medication adherence, will be measured using several approaches – self-report (ARMS; MedTake Assessment), which is easier and cheaper, and objective (pill count; electronic medication packaging [EMP]), which is tedious and expensive – during the 2 pilot trials. Comparison of the various approaches against the EMP (the most objective approach) will inform the choice of the measurement approach to be used for medication adherence in the larger RCT.

#### 3. EXPECTED RIKS AND BENEFITS

Risks to participants are expected to be minimal in the study:

(1) Potential risk from breach of confidentiality: Exposure of patient-related information such their personal details and medical information (including medication they are taking, medication-adherence scores)

Expected benefits are as follows:

(1) Improved medication-related outcomes: Provision of bilingual PMLs through the study is expected to improve the following 3 areas for participants- medication adherence, medication management self-efficacy, and PML understanding. Improvements in these 3 areas will enhance the benefits patients will receive from their medication therapy, resulting in greater medication-related outcomes.

#### 4. STUDY POPULATION

#### 4.1. List the number and nature of subjects to be enrolled.

A total of 40 patients will be recruited from Singapore General Hospital's outpatient clinics, which is the only study site involved. There will be no subject restrictions based on race of the subject, but as per the inclusion criteria set out in section 4.3 below, they should be able to speak English and/or Mandarin, and unable to read in English but able to read Mandarin (as they will benefit the most from bilingual PMLs).

#### 4.2. Criteria for Recruitment and Recruitment Process

Patients who meet all the inclusion criteria set out in section 4.3 below and do not meet any of the exclusion criteria set out in section 4.4 below are eligible to be recruited into the study. Suitable patients will be identified by either the patient's primary physician or by a pharmacist at Diabetes and Metabolism Centre (DMC) pharmacy. These suitable patients will be introduced to the study and if they express interest, they will be referred to the research assistant for consent taking, administration of the baseline covariate questionnaire and randomisation to study group.

#### 4.3. Inclusion Criteria

[figure not shown]
(1) Singapore Chinese citizen/permanent resident; (2) age  $\geq$ 50 years; (3) just received a new (i.e., not received before) oral medication for a chronic disease from DMC pharmacy; (4) no moderate/severe cognitive impairment ( $\geq$ 5 correct responses on the Abbreviated Mental Test, AMT); (5) not deaf (self-reported); (6) no binocular presenting near vision impairment (near visual acuity, with routinely used spectacles/lenses: at least 6/15 (0.40 logMAR) on the Landolt's C chart); (7) able to speak English and/or Mandarin; (8) unable to read in English but able to read Mandarin (as they will benefit the most from bilingual PMLs); (9) assessed as non-adherent as per 2 questions - "In the last one month, how often did you take your medications?" (as they will benefit the most from an intervention aimed at improving medication adherence).

#### 4.4. Exclusion Criteria

(1) Patients who received, from the prescribing physician, a set of instructions for their new oral medication that does not match standard instructions (as the bilingual instructions for non-standard instructions would not be prepared for beforehand)

#### 5. STUDY DESIGN AND PROCEDURES/METHODOLOGY

This is a 2-arm open-label parallel-group RCT with 2 versions (Pilot Trial A, and Pilot Trial B). A total of 40 eligible patients, after informed consent, will be randomized (1:1; block randomization, block of 4) in the DMC pharmacy to either Pilot Trial A or Pilot Trial B (Figure 2).

\* Study procedures have been modified slightly in view of prevailing COVID-19 control measures. Please refer to section 5.1.1 for a detailed methodology.

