#### 5.1 Study Design

Briefly, in Pilot Trial A, all will be first given the usual English PML for their new medication. There may be non-standardized, ad-hoc noting on the PML by the pharmacy staff when participant is deemed not able to understand the English PML. All content of the non-standardized, ad-hoc noting including pictures drawn will be recorded. Then, *at 2 weeks post-recruitment*, their baseline level of the 3 medication-related outcomes (w.r.t. the new medication) will be gauged, after which they will be *randomized* (1:1; block randomization, block of 4) to one of 2 PMLs (Bilingual [intervention] or English [usual care]) at their home. Follow-up assessment of the 3 medication-related outcomes will be also be done at 2 weeks post-randomization at their home.

In Pilot Trial B, participants will be *randomized* (1:1; block randomization, block of 4) *just after recruitment* to one of 2 PMLs (Bilingual [intervention] or English [usual care]) in the DMC pharmacy. There may be non-standardized,ad-hoc noting on the PML by the pharmacy staff when participant is deemed not able to understand the English PML. All content of the non-standardized, ad-hoc noting pictures drawn will be recorded. The 3 medication-related outcomes will be assessed at 2 weeks post-randomization at their home.

All participants will receive their usual medical care, and usual medication counselling at the DMC pharmacy for all their medications. All medications, other than the new oral medication (which made them eligible, and whose PML will be intervened upon), will be dispensed with usual English PMLs.

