#### 5.2 Study Methodology

Bilingual PMLs (Intervention): Bilingual PMLs, for common medications at the DMC pharmacy, which "mirror" medication instructions on the corresponding English PMLs, will be developed by the investigator team. While the Health Products (Therapeutic Products) Regulations 2016 mandate English PML provision, there is no restriction to adding another language. In fact, some polyclinics already print PMLs in their patients' preferred language, upon request, to supplement English PMLs.

Randomization: All 3 block randomization sequences (Pilot Trial A or B, then, study arm within each Pilot Trial) will be generated a priori. After a participant gives consent, project staff will be informed of his/her allocation to Pilot Trial A or B. For those in Pilot Trial A, further assignment to study arm will be disclosed only after the baseline level of the 3 medication-related outcomes is assessed at 2 weeks post-recruitment. For those in Pilot Trial B, assignment to study arm will be disclosed immediately, as there is no baseline assessment of the 3 medication-related outcomes.

Covariates: A range of socio-demographic and medication-related (e.g. no. of medications, help received in medication management) variables will be collected, using a questionnaire, at recruitment.

Medication-related outcomes: They will be gauged at 2 weeks post-recruitment and 2 weeks post-randomization for those in Pilot Trial A, and at 2 weeks post-randomization for those in Pilot Trial B.

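### A fixed block of 4, printed in the protocol of an open-label single-site trial, lets staff who keep track deduce about one allocation in three, including the Pilot A arm before its baseline assessment

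*Protocol*

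**What the plan says.** Section 5 of the protocol describes the design: "This is a 2-arm open-label parallel-group RCT with 2 versions (Pilot Trial A, and Pilot Trial B"). The 40 consenting patients "will be randomized (1:1; block randomization, block of 4) in the DMC pharmacy to either Pilot Trial A or Pilot Trial B". Section 5.1 then allocates Pilot A patients, two weeks later and after their baseline outcomes, ("1:1; block randomization, block of 4) to one of 2 PMLs (Bilingual [intervention] or English [usual care]) at their home"). Pilot B patients are allocated to a label with the same ratio and block size straight after recruitment. Section 4.1 recruits from "Singapore General Hospital's outpatient clinics, which is the only study site involved", and no stratification factor is stated, so each of the three steps runs from a single list.

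Section 4.2 has a physician or a pharmacist identify patients, who if interested are "referred to the research assistant for consent taking, administration of the baseline covariate questionnaire and randomisation to study group". Section 10 gives the research assistant the protocol and responsibility for carrying it out.

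Section 5.2 has all three sequences generated in advance. Project staff learn the pilot version once consent is given. In Pilot A, "further assignment to study arm will be disclosed only after the baseline level of the 3 medication-related outcomes is assessed at 2 weeks post-recruitment". The protocol describes no varied or masked block size and no blinded assessor.

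**The concern.** In a block of 4 at 1:1, once one treatment has been used twice the rest of the block is known. Withholding the list does not hide this from someone who knows the block size and has seen the earlier results. Here the size is in print, treatment is open, and project staff are told each result.

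In Pilot A the delayed disclosure evidently serves to have the baseline measured without knowledge of the arm. Several baseline measures in sections 5.2.1 come from an interview: ARMS, MedTake, the self-efficacy scale and the label-understanding questions. Section 8.2 compares the arms on change from that baseline, so an assessor's expectation would enter the contrast directly.

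The second route is at consent. The research assistant could foresee whether the next patient falls into Pilot A or B. Pilot A asks for an additional assessment. Section 2 uses the study to decide which version to scale up, and section 8.2 tabulates participation and loss to follow-up. Selective encouragement would distort that comparison.

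**Working it through.** The protocol gives no figure for predictability, so there is none to reproduce.

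**Inputs.** Block of 4 at 1:1 for all three sequences (sections 5 and 5.1); 40 patients, hence 20 per pilot (section 5); one site (section 4.1). Assumed: staff know the block size, and the earlier allocations in the block have been disclosed to them by the time of the next patient.

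**Step 1: certain allocations.** There are C(4,2) = 6 possible blocks. Two of them (AABB, BBAA) have 2 forced allocations each; the other four (ABAB, ABBA, BAAB, BABA) have 1 each. Forced: 2×2 + 4×1 = 8 of 6×4 = 24, which is 1/3, or 4/3 per block. The first two positions are never certain, the third is certain in 1/3 of blocks, and the fourth always is.

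**Step 2: patients affected.**
- Pilot A or B: 40/4 = 10 blocks; 10 × 4/3 = 13.3 of 40.
- Arm within each pilot: 20/4 = 5 blocks; 5 × 4/3 = 6.7 of 20.

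A simulation of the three-list design (50,000 runs) gave 33.3% at each step.

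**Step 3: best guess.** The rule is to name the treatment used less so far in the block, and to toss a coin when level. The chances of being right at positions 1 to 4 are 1/2, 2/3, 2/3 and 1. (At position 3, the block is level with chance 2/3 and settled with chance 1/3: 2/3 × 1/2 + 1/3 × 1 = 2/3.) The mean is (1/2 + 2/3 + 2/3 + 1)/4 = 17/24 = 70.8%, against 50% by chance.

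**Step 4: what can be foreseen before consent.** In the same simulation, the version was certain beforehand for 6.7 of the 20 Pilot B patients. Version and label arm were both certain for 2.8 of 20, about 14%. In Pilot A the patient is already enrolled when the arm is allocated, so a foreseen arm cannot steer enrolment.

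**Step 5: alternatives.**

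| Scheme | Certain | Guessed correctly |
|---|---|---|
| Fixed block of 4 | 33% | 71% |
| Fixed block of 6 | 25% | 68% |
| Fixed block of 8 | 20% | 67% |
| Random mix of 4 and 6 | about 6% | 68 to 69% |
| One block of 20 per pilot | 9% | 62% |

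The mixed-block row is simulated and assumes that staff know the permitted sizes but not their order. Its mean arm difference at 20 patients is about 0.5. The difference can never exceed 3, because that is the most by which an unfinished block of 6 can be out.

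For one block of 2m = 20, the expected number of certain allocations is 2m/(m+1) = 20/11 = 1.8, which is 9.1%. Expected correct guesses are m + (4^m/C(2m,m) − 1)/2 = 10 + (1,048,576/184,756 − 1)/2 = 12.3, which is 61.7%.

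**Step 6: balance with one block of 20.** It gives 10 v 10 only if all 20 are randomised. If, as an assumption, 14 are, the chance that the arms differ by 4 or more is 1 − [C(10,7)² + 2·C(10,6)·C(10,8)]/C(20,14) = 1 − (14,400 + 18,900)/38,760 = 14%. With 16 randomised it is 1 − [C(10,8)² + 2·C(10,7)·C(10,9)]/C(20,16) = 1 − (2,025 + 2,400)/4,845 = 9%. Blocks of 4 cap the difference at 2.

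**The case against.** The case for leaving the plan alone is that a fixed block of 4 is a common and internally consistent choice for 40 patients, and that most routes from predictability to bias are narrow. Much of this stands, and it rules out several stronger readings that a reader might reach.

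- *That allocation is unconcealed.* The protocol says open-label. Section 5.2 withholds the version until after consent and the Pilot A arm until after the baseline. What remains is deduction, not sight of the list.
- *That the research assistant chooses whom to approach.* Section 4.2 gives identification and introduction to physicians or pharmacists, and nothing says that they follow the running sequence. The assistant could still influence consent.
- *That a third of patients could be selected into a label arm.* The first step allocates to a pilot version. For Pilot B, version and arm are both certain before consent for only about 14%; for Pilot A, arm-based selection is impossible.
- *That the Pilot A safeguard is defeated outright.* Two thirds of arms remain uncertain at baseline, participants themselves do not know theirs, and the pill count and cap openings leave an assessor little room. Understanding items are also marked simply right or wrong.
- *That the same person recruits and assesses.* Sections 5.1.1 and 6.3 speak only of study or research staff at the visits. Section 10 makes it plausible, no more.

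Section 2 also disclaims any aim of showing a significant difference, section 8.2 calls most analyses descriptive and exploratory, and the comparison of adherence measures does not depend on arm. None of this removes the exposure of the interview-based Pilot A baseline, or the fact that the block size is printed where recruiting staff will read it.

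**Conclusion.** The point holds in a limited form. With a fixed, published block of 4, one allocation in three is certain on average at each of the three steps, and 71% can be guessed. The main consequence is that about 6.7 of 20 Pilot A arms can be deduced before a baseline meant to be taken without that knowledge. Foreseeing Pilot A or B at consent is secondary.

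These figures are expectations. They require staff who know the block size and keep track, and, for Pilot A, that earlier arms in the block are already disclosed at the time of the visit. They measure opportunity; the documents give no basis for the size of any resulting bias. Because the study is chiefly about feasibility, this is a cheap improvement of low to moderate priority. It matters most if the procedure is carried into the larger trial.

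**What to change.** Generate the three lists with randomly mixed block sizes, for example 4 and 6. Replace the block size in sections 5 and 5.1 by a statement that permuted blocks of varying size are used, and hold the sizes in a restricted randomisation file that recruiting and assessing staff do not see. Release each assignment only when it is due, as section 5.2 already provides.

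The lists are made in advance anyway, so the cost is small if they are not yet in use: regenerating them and editing the text. The gain is in certainty rather than in guessing. Certain allocations fall from 33% to about 6%, guessing only from 71% to about 68%. The downside is a small possible imbalance, about 0.5 patients on average at 20.

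A single block of 20 per pilot is not preferred. It is harder to guess, but Pilot A randomises two weeks after recruitment, and sections 5.1.1 and 5.2.2 provide for forfeiture and withdrawal in between, so equal arms cannot be counted on.
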